## **Statistical Analysis Plan**

In the PRIME study (29), eight risk factors for medication-related harm (MRH) were identified: gender, age, past adverse drug reactions, antiplatelet drug, antidiabetic drug, living alone after discharge, Sodium level (mmol/L) and total number of medicines at discharge. These variables will be explored further in the proposed study. The univariate summaries of these variables will be provided and compared between participants in the control arm and participants in the intervention arm.

Baseline characteristics of participants included in the study will be analysed (using aggregated data and for data stratified by certain demographic characteristics) for descriptive purposes only.

Important variables known to be associated with MRH will also be described by randomisation groups. These variables will be taken into account in the analysis by fitting one multivariable logistic regression incorporating these variables to the data.

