## 5 STUDY DESIGN AND METHODS OF DATA COLLECTION AND DATA ANALYSIS

Participants will be recruited across 4 sites: Royal Sussex County Hospital in Brighton, Ashford and St Peter's Hospital in Ashford, Medway Hospital in Kent, and Royal Devon Hospital in Exeter. The proposed study is a Randomised Control Trial (RCT), as patients will be randomised into either the NHS DMS alone (control arm/standard care), or RPT-stratification plus MMP linked to the NHS DMS (intervention arm).

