## Sample size/power details

In determining the sample size, let the proportion of subjects developing MRH when given the standard care be  $p_1$ , while the proportion of subjects developing MRH among those put through intervention arm be  $p_2$ . Common measures for comparing whether the two proportions are statistically significantly different are:

- 1. Difference,  $\delta = p_1 p_2$
- 2. Odds-ratio,  $\Psi = \frac{p_1/(1-p_1)}{p_2/(1-p_2)}$

Then the two equivalent hypotheses for evaluating whether the two proportions are different are H0: $\delta$ =0 and H0: $\Psi$ =1. The values of  $\Psi$  close to 1, indicate no difference and those further from 1 are the ones that specify differences that may be clinically important. The sample size formula can be expressed so that the only parameters needed are the prevalence of MRH in the population receiving standard care and odds-ratios and there is no need to directly incorporate  $\delta$  in calculations. In this case  $\Psi$  is the fixed parameter and sample size can be calculated for various values of prevalence. The advantage of using the odds-ratios as fixed is that it is straightforward to define clinically important differences from a range of admissible values. Once desired value of odds-ration is selected, the corresponding values of  $\delta$  (defining clinically important difference), can be computed for the observed prevalence value.

The choice of the value of odds-ratio to use is based on the range of values of odds-ratios that normally show up as significant in statistical analyses. As it is not expected that the two arms of the study would be dramatically different, we recommend the choice of medium values of odds-ratios.

A systematic review of MRH in older adults found that between 17% and 51% of patients experience MRH within 30 days of hospital discharge. In the UK, approximately 28% of older adults ( $\geq$ 65 years) use health services due to MRH within the 8 weeks following hospital discharge (6). Therefore, our choice of the prevalence to use in the sample size calculation is limited to MRH rates between 20% - 40%. In particular, we take the prevalence of MRH among the group under standard treatment to be 35% and an odds-ratio of 1.6 is considered large enough to result in a clinically important difference in MRH rates between arm 1 and arm 2. These choices of  $p_1$  and odds-ratio corresponds to  $\delta$ =0.098.

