To determine the required sample size to estimate a difference  $\delta$  that is clinically relevant, the method of Fleiss, Tytun, and Ury (53) was used. This method has been implemented in the function "bsamsize" given in R package "Hmisc" (54). To calculate sample size using this method, one needs to provide the following parameters: the prevalence of MRH among people given standard treatment ( $p_1$ ) and among people given the new care/intervention ( $p_2$ ), odds-ratio ( $\Psi$ ), the statistical power we wish to achieve, and the margin of error.

We found that a sample size of n=682 (341 subjects on each arm) will be required to detect  $\delta$ =0.098 (i.e., odds-ratio=1.6), with 80% statistical power, and a 5% margin of error, if we assume that the prevalence of MRH among those on standard treatment is 35%.

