## 7.2 Sampling and Recruitment

#### 7.2.1 Sampling technique

After enrolment, participants will be randomised to either the intervention or group receiving standard treatment: a 1-to-1 ratio stratified by site, with allocations permuted between blocks. The randomisation sequence will be created using the R software package (54): "randomizeR", a program that generates randomized equi-probable sequences through a procedure called Permuted Block Randomization (PBR) with block constellation. The parameters involved include: the block constellation, the number of treatment groups (in our case, 2), and the vector of the ratio (which in our case is a vector with two elements, which are both 1's).

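### Randomisation is stratified by site, but the one logistic regression described does not name site; adding it, with a standardised risk difference, is a small and free improvement

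*Protocol*

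**What the plan says.** - **Randomisation.** Protocol Section 7.2.1 allocates participants in "a 1-to-1 ratio stratified by site, with allocations permuted between blocks". No other stratification factor is given. Section 5 states: "Participants will be recruited across 4 sites". Section 7.2.2 and Table 1 of the appendix allow one or two more sites if recruitment lags.
- **Analysis.** The text headed Statistical Analysis Plan in Section 5.1 first lists the eight PRIME risk factors, to be summarised and compared between arms. A later paragraph says: "Important variables known to be associated with MRH will also be described by randomisation groups". It continues: "These variables will be taken into account in the analysis by fitting one multivariable logistic regression incorporating these variables to the data". That paragraph gives no closed covariate list. Site is not mentioned as a model term, and no stratified analysis is described elsewhere in the protocol.
- **Planning effect.** Under Sample size/power details, "we take the prevalence of MRH among the group under standard treatment to be 35" per cent, and "an odds-ratio of 1.6 is considered large enough to result in a clinically important difference in MRH rates". This corresponds to a difference of 0.098 and gives 682 participants "with 80% statistical power, and a 5% margin of error".

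**The concern.** An analysis normally reflects the factors used to restrict the randomisation. Blocking within site forces the arms to be balanced within each site, so the true sampling variation of the treatment comparison is smaller than it would be under simple randomisation. A model that leaves site out cannot use this. If site is related to MRH, its standard error is a little too large for what it estimates, and the test becomes conservative. The odds ratio it estimates is also averaged over sites, which puts it nearer to 1 than the within-site odds ratio.

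Site could well be related to MRH. The process evaluation (Section 5.3) expects organisational variation between sites, and each site has its own pharmacists collecting outcome data (Table 1). There is little slack to absorb a loss: the planned power is 80% and the recruitment target equals the calculated sample size.

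A second, related issue is scale. The clinically important effect is defined from two arm proportions, which is a marginal contrast. A covariate-adjusted odds ratio is conditional, so it cannot be read directly against 0.098.

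**Working it through.** **Inputs from the protocol.** Control rate p1 = 0.35; odds ratio 1.6 (standard care over intervention); 341 per arm; 80% power; 5% level; four sites; allocation balanced within site. **Assumed, because the protocol does not give them:** the between-site SD of the log-odds of MRH (varied from 0.2 to 0.75), equal site sizes, and the spread of the patient risk score.

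**Step 1: reproduce the sample size.**
- p2 odds = (0.35/0.65)/1.6 = 0.3365, so p2 = 0.3365/1.3365 = 0.2518 and δ = 0.0982.
- n per arm = [1.96·√(2p̄(1−p̄)) + 0.842·√(p1(1−p1) + p2(1−p2))]² / δ², with p̄ = 0.3009. This gives 341.2.
- Rounded, that is 341 per arm, or 682 (rounding up gives 684). Power at 341 per arm is 79.97%. The figure reproduces as two-sided without continuity correction; with the correction it would be 724.

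**Step 2: large-sample effect of leaving site out.** Control rates average 35%, site log-odds are evenly spaced with SD σ, and the within-site odds ratio is 1.6 (log 0.470).
- *Site omitted.* With arm averages Pc and Pt, b = logit(Pc) − logit(Pt). SE_model = √[1/(nPc(1−Pc)) + 1/(nPt(1−Pt))]. SE_true replaces each binomial variance by the mean within-site variance. Power = Φ((b − 1.96·SE_model)/SE_true).
- *Site included.* SE = 1/√Σw, where w = 1/[1/(m·pc(1−pc)) + 1/(m·pt(1−pt))] for each site and m = 341/4. Power = Φ(0.470/SE − 1.96).
- *Type I error, site omitted.* 2[1 − Φ(1.96·SE_model/SE_true)], evaluated at odds ratio 1.

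Worked example at σ = 0.3: Pc = 0.350, Pt = 0.2534, b = 0.4614, SE_model = 0.1685, SE_true = 0.1670. Power without site is Φ((0.4614 − 0.3302)/0.1670) = 78.4%. With site, SE = 0.1701 and power is Φ(2.763 − 1.96) = 78.9%.

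| σ | Site control rates | OR, site omitted | Log OR shrinks by | Power: omitted → included | Loss (points) | Type I error, omitted |
|---|---|---|---|---|---|---|
| 0.2 | 29–41% | 1.594 | 0.8% | 79.0 → 79.3% | 0.2 | 4.9% |
| 0.3 | 26–44% | 1.586 | 1.8% | 78.4 → 78.9% | 0.5 | 4.8% |
| 0.5 | 21–50% | 1.563 | 4.9% | 76.3 → 77.7% | 1.5 | 4.4% |
| 0.75 | 15–58% | 1.525 | 10.3% | 72.1 → 75.5% | 3.4 | 3.8% |

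Losses are taken before rounding. With no site variation this Wald calculation gives 79.6%. At σ = 0.37 (rates 24–46%) the loss is 0.8 points. A spread about as wide as the protocol's 20–40% planning range therefore costs under 1 point.

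**Step 3: simulation.** 4,000 trials per scenario, both models also adjusting for a risk score with assumed SD 0.8 on the log-odds scale. Power without and with site: 75.3% and 76.0% (σ = 0.3), 72.7% and 74.0% (0.5), 66.2% and 70.2% (0.75). Type I error without site was 4.7%, 4.8% and 4.3%. With site it was 4.9%, 5.6% and 5.5%, within two Monte Carlo standard errors of 5% (one is about 0.34 points).

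**Step 4: scale.** Averaging over a normal risk score with the control rate held at 35%, the planned marginal difference of 0.098 corresponds to a conditional odds ratio of about 1.64, 1.67 or 1.75 for an assumed risk-score SD of 0.5, 0.7 or 1.0. An adjusted odds ratio of exactly 1.6 would correspond to a difference of 0.094, 0.090 or 0.084.

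**The case against.** The strongest reply is that the protocol is silent on site and does not exclude it. The covariate description is open, the eight PRIME factors stand in a separate paragraph, and a prognostic site effect could fall within the wording. Exact model terms are often left to a separate analysis plan, which is not available here. This stands, and it limits the point: the text does not say that the model adjusts only for PRIME variables. What remains is that the protocol describes one model under its own analysis heading and does not name the factor it stratified on.

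Several stronger readings are tempting, and the documents do not support them:
- *Leaving site out loses precision.* In a logistic model the standard error of the log odds ratio rises when site is added (0.1685 to 0.1701 at σ = 0.3). What is lost is a little power.
- *The odds ratio is biased.* The shift is non-collapsibility: a different odds ratio, averaged over sites. The randomised comparison itself is sound.
- *The trial is really planned on 0.090.* The protocol derives 1.6 from two arm proportions, so 1.6 is marginal and belongs with 0.098. The smaller figure arises only if 1.6 is read as conditional.
- *Sites may range from 17% to 51%.* The protocol gives that as a range across studies in a systematic review at 30 days. It says nothing about these four hospitals at 8 weeks.

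A standardised questionnaire and pharmacist training also reduce differences between sites in how MRH is judged, and adjusting for risk factors absorbs part of any case-mix difference. Both support the smaller values of σ.

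**Conclusion.** The point holds as a minor matter of specification. Following the described model without site gives a slightly conservative test and an odds ratio slightly closer to 1. The power loss is under 1 point for site differences of about the width of the protocol's planning range, and about 1.5 to 3.5 points for larger ones (1.3 to 4.0 in the simulation). All of these sizes rest on an assumed between-site variation. Type I error is not inflated, the sample size is unaffected, and the validity of the trial is not in question. The scale point is a matter of reporting: without a marginal estimate, an adjusted odds ratio of 1.6 could be misread as meeting the planned difference of 0.098.

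**What to change.** In the Statistical Analysis Plan text of Section 5.1, state the primary model as logistic regression of MRH on arm, site and the eight named PRIME variables. Site should be a fixed effect with one level per recruiting site, including any opened under the contingency.

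From the same model, report the adjusted odds ratio together with the standardised risk difference and its 95% CI. That difference is obtained by predicting each participant's risk under both arms, averaging within arm and subtracting, and it can be read against 0.098.

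The cost is a sentence or two. Site is known for everyone. Four sites add three parameters (five if two sites are opened) against about 205 expected events (341 × 0.35 + 341 × 0.2518 = 119 + 86). The sample size does not change. The wording should be settled before outcomes are seen by arm. If a separate analysis plan already specifies this, a pointer in the protocol is enough.

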## **5.2 ECONOMIC**

## **Economic Evaluation**

The economic analysis will adopt the perspective of health and personal social services. Resources involved in delivering the interventions will be gathered prospectively. A researcher will observe the RNs and pharmacists involved in undertaking risk assessments and creating Medicines Management Plans in order to establish the time involved. Initially, time measurements will be obtained for a random sample of 25 participants with the sample being increased if high variability is observed. As in the original PRIME study, service use associated with incidents of medication-related harm will be collected retrospectively from three sources: phone interviews with participants, GP records and hospital records, including A&E attendance, hospital re-admissions, outpatient, GP, community care and social care. Costs of service use and the intervention will be based on validated national sources (PSSRU; National Reference costs) (49). Costs will be compared between groups and modelled to provide national estimates (50).

#### **5.3 PROCESS**

#### **Process Evaluation**

This work package will include data collection and analysis from qualitative focus group interviews of researchers and service providers based on the need to investigate the acceptance and use of the study processes in both the control and the intervention arms. The evaluation will explore the context of implementation of the proposed intervention in the four study sites: Royal Sussex County Hospital in Brighton, Ashford and St Peter's Hospital in Ashford, Medway Hospital in Kent, and Royal Devon Hospital in Exeter. The focus of interviews will be based on previous studies of new ways of working to enhance medicines management that sought to include practitioner understanding in the adoption (51), and the development of recommendations to inform the scaling and sustainable roll-out of the protocol in further study in practice. Normalisation process theory enables learning about the use of a new tool within existing practices and shapes learning about the organisational receptivity.

#### Interviews:

It is known that pharmacy interventions with older people increase safety (52), and the interview schedule /topic guide in the proposed study will investigate the context, perceived outcomes, and delivery of the study intervention by interviewing healthcare providers in hospital and the community (a group of doctors, pharmacists, nurses, and commissioners). There is a background knowledge associated with the benefits of using PRIME-RPT that will be shared with the PCIE group. The results of the process evaluation will be discussed with the PCIE committee.

#### Sampling:

Purposive sampling will include where possible a matched sample of 6-9 interviews in each site (Brighton, Ashford, Exeter and Kent) including service providers, and researchers: study nurses and pharmacists, geriatricians, senior operational managers and in addition external stakeholders in CCGs and potentially in community services or primary care. It is assumed that each context will have a variation in organisational form but also similarities in relation to best practices in discharge management and medicines management. Process evaluation will include this variance in relation to individual sites. Links with the CCGs will be facilitated by [name], a member of the National Adoption committee in the study.

## Data collection:

Focus group interviews with researchers and service providers will be undertaken by Zoom/MS Teams and are expected to last 45-60 minutes and will be based on a semi structured interview topic guide. The meetings will be audio/ video recorded and notated with key quotations italicized by the RA. The trial coordinator will set up the interviews on behalf of the process evaluation team, at the convenience of both parties.

#### Timeline:

The initial meeting with the 4 sites will include discussion about the process evaluation – identifying key stakeholders who are responsible for the study. Data collection will take place midway through the project and the analysis will align to the final study report led by [name] (KA).

## 6 STUDY SETTING

This is a multicentre study across 4 hospitals: Royal Sussex County Hospital, Medway Maritime Hospital, Royal Devon and Exeter NHS Foundation Trust and Ashford and St Peter's Hospital.

In each hospital, patients aged 65 and older due for discharge in 48 hours will be approached by a research nurse. This is appropriate research setting to acquire a sample representative of our target population.

Study participants will be followed up for 8 weeks post-discharge.

## 7 SAMPLE AND RECRUITMENT

#### 7.1 Eligibility Criteria

#### 7.1.1 Inclusion criteria

- Patients must be over the age of 65 years at the time of recruitment, admitted to an acute Elderly Care or General Medical Ward,
- Patients to be identified when they are likely to be discharged within 48 hours.
- Patients need to be registered with a General Practitioner within the areas covered by the recruiting hospitals.
- Informed written consent must be provided from patients with capacity OR personal consultees acting on behalf of patients without capacity

## 7.1.2 Exclusion criteria

- Patients lacking capacity and have no consultee to advise
- Patients that are transferred to other acute healthcare trusts (but excluding step down or intermediate care facilities)
- Patients who have a short life expectancy, due to a terminal illness
- Patients who are unable to read/speak/understand English

## 7.2 Sampling and Recruitment

#### 7.2.1 Sampling technique

After enrolment, participants will be randomised to either the intervention or group receiving standard treatment: a 1-to-1 ratio stratified by site, with allocations permuted between blocks. The randomisation sequence will be created using the R software package (54): "randomizeR", a program that generates randomized equi-probable sequences through a procedure called Permuted Block Randomization (PBR) with block constellation. The parameters involved include: the block constellation, the number of treatment groups (in our case, 2), and the vector of the ratio (which in our case is a vector with two elements, which are both 1's).

## 7.2.2 Recruitment

In each hospital, the research nurse will approach patients aged 65 years and over about to be discharged in the next 48 hours. We are confident that in each of the 4 hospital sites, six patients can be recruited each week in view of the ease of screening and recruiting study participants. At this rate, 24 patients can be recruited weekly from the 4 hospital sites, equating to 96 patients per month. Consequently, we will be able to recruit 684 patients to the study from the 4 sites in approximately 7.5 months. Our sample size is 682 patients. The research nurse and trial pharmacist will work in collaboration with hospital and primary care clinical teams (GPs and community pharmacists) and the DMS service teams to ensure study recruitment and data collection is achieved according to time and target.

Recruitment targets will be monitored closely by the study advisory committee. In addition, we do have a contingency plan to open 1-2 additional sites if recruitment from the initial 4 sites is not achieving the target of 96 patients per month. The risk-assessment strategy described below will enable us to accomplish our target in the proposed timeline. (See Table 1 in Appendix)

## 7.3.1 Sample identification

The research nurse will visit the elderly care and general medical wards daily and will liaise with the medical team to identify those eligible participants. The clinical team will inform potential participants about the study, and if they express an interest in taking part, the research nurse will approach them. The research nurse will approach patients aged 65 years and older who are due to be discharged from the acute Care of the Elderly and General Medicine wards and fit inclusion/exclusion criteria.

## 7.3.2 Consent

The research nurses will be trained on requesting consent from potential participants. The participant will be provided with a participant information sheet and the research nurse will explain the study to them. They will be given the opportunity to ask questions, and the time to consider their participation up until the point of discharge. Informed written consent will be sought.

If a potential participant lacks capacity to consent, a family member/friend/carer will be asked to act as a personal consultee and to support the potential participant taking part in the study. If the potential participant regains capacity prior to discharge, they will be invited to take part in the study. It is important to include those who lack capacity, as we do not wish to exclude those who are most likely to experience MRH i.e. those most vulnerable due to frailty and/or cognitive limitation. If a potential participant lacks capacity and a suitable personal consultee is not available, they will not be included in the study.

Continued consent will be assumed throughout the 8-week study period. There will only be a maximum of three points of contact with the research team; firstly, on joining the study, secondly at the end of the 8-week study period and, thirdly, in the case that they are re-admitted within the 8 weeks.

Participants with capacity will be asked to provide a family member/relative/friend to contact, in case that they lose their capacity if they are re-admitted or at the 8-week phone call. This will be needed in case that the family member/relative/friend needs to be contacted, to act as a consultee to consent for the patient who has lost capacity for continued participation. The patient will be withdrawn if there is no consultee, if the consultee decides to withdraw the individual from the study or if the participant themself wishes to be withdrawn. For participants who lack capacity, a phone call or Zoom interview will be conducted with their carers/consultees.

